6.2.5. Treatment-related Lymphocytosis

Treatment-related lymphocytosis, for the purposes of this protocol, is defined as an elevation in blood lymphocyte count of \geq 50% compared to baseline that occurs in the setting of improvement in at least one other disease-related parameter and is associated with agents known to inhibit BCR (see Section 8.1.5 for additional details) (Hallek 2012, NCCN 2012, Cheson 2012). Given the known mechanism of action of BCR-inhibiting agents including ibrutinib, treatment-related lymphocytosis is an expected and frequent pharmacodynamic phenomenon observed with initiation (or re-initiation) of ibrutinib. Ibrutinib associated treatment-related lymphocytosis generally occurs within the first weeks of therapy, peaks within the first few months, and resolves slowly. Asymptomatic treatment-related lymphocytosis should not be considered an AE and patients should remain on study treatment.

Specifically, upon initiation of treatment, a transient phase of increase in lymphocyte counts (ie, $\geq 50\%$ increase from baseline and above absolute count of $5,000/\mu\text{L}$), often associated with reduction of lymphadenopathy, has been observed in most patients (75%) with relapsed/refractory CLL/SLL and some patients (33%) with relapsed/refractory MCL treated with ibrutinib monotherapy. This observed transient lymphocytosis is usually not associated with an adverse event and should not be considered progressive disease in the absence of other clinical findings. In both disease types, lymphocytosis typically occurs during the first few weeks of ibrutinib therapy (median time 1.1 weeks) and resolves within a median of 7.1 weeks in the MCL and 18.7 weeks in the CLL patients.

A substantial increase in the number of circulating lymphocytes has been observed in a subset of patients. There have been isolated cases of leukostasis reported in patients treated with ibrutinib.

A high number of circulating malignant cells ($\geq 400,000/\mu\text{L}$) may confer increased risk; these patients should be closely monitored. Administer supportive care such as hydration and/or leukopheresis as indicated. Ibrutinib may be temporarily held, and Medical Monitor should be contacted.

6.2.6. Dose Modification for Hepatic Impaired Subjects

Ibrutinib is metabolized in the liver and therefore subjects with clinically significant hepatic impairment at the time of screening (Child-Pugh class B or C) are excluded from study participation. For subjects who develop mild liver impairment while on study (Child-Pugh class A), the recommended dose reduction for ibrutinib/placebo is to a level of 280 mg daily (two capsules). For subjects who develop moderate liver impairment while on study (Child-Pugh class B), the recommended dose reduction is to a level of 140 mg daily (one capsule). Subjects who develop severe hepatic impairment (Child-Pugh class C) must hold study drug until resolved to moderate impairment (Child-Pugh class B) or better. Monitor subjects for signs of toxicity and follow dose modification guidance as needed (Refer to [Appendix L](#)).

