The Follow-up Phase will be comprised of 2 phases; the Post-treatment Phase and a Post-disease Progression Phase. The Post-treatment Phase will extend from the discontinuation of treatment up until the patient has progressive disease or other criteria listed in [Section 10.1](#). Response

evaluations will be continued every 12 weeks from the initial dose with study drug until 18 months and then every 24 weeks until disease progression.

The Post-disease Progression Phase will begin once a patient has progressive disease. In this phase, subsequent anticancer therapy with start date of therapy, IWCLL indication for treatment initiation, additional malignancy occurrence, and patient survival status will be recorded. The Post-disease Progression Phase will continue until death, lost to follow up, consent withdrawal, or study closure, whichever occurs first. It is important that survival status be assessed and that the date of death is documented for each patient randomized to treatment, regardless of whether or not the patient received treatment.

Assessment of response and progression will be conducted in accordance with the IWCLL 2008 criteria with the modification that treatment-related lymphocytosis in the absence of other signs or symptoms of disease progression will **not** be considered progressive disease ([Section 8.1.5](#)). The Investigator will evaluate sites of disease by radiological imaging (primary), physical examination or other procedures as necessary, review of hematology and serum chemistry results, and disease-related symptoms. The same methods of assessment used to assess disease at baseline should be used throughout the study. A central laboratory will perform all hematology and serum chemistry testing for the primary endpoint analysis. The primary efficacy analysis will be based on assessment from an IRC. As part of the IRC review, radiographic evaluations assessed by independent central radiologists and hematology results from a central laboratory will be provided. Detailed procedures will be described in a separate charter.

An independent Data Monitoring Committee (DMC) will be formed and constituted according to regulatory agency guidelines. Detailed information regarding the composition of the DMC and detailed DMC procedures will be provided in a separate charter. The DMC will review the safety data periodically and the interim analysis results and provide recommendations according to the charter.

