7.3.2.5. Week 4-24 Visits, every 4 weeks

The following procedures will be performed:

- Administration of ofatumumab or ibrutinib
- Physical examination
- Eye-related symptoms (Weeks 12 and 24)
- Disease-related symptoms (no longer required per Amendment 5)
- Vital signs
- ECOG performance status
- PRO assessments
- Concomitant medications
- Adverse events
- Hematology
- Serum chemistry
- Sparse PK sample (ibrutinib arm - Week 4 only)
- T/B/NK cells (Weeks 12 and 24)
- Flow cytometry-based immunophenotype assays (Beginning at Week 8)
- Serum immunoglobulins and β 2-microglobulin (Weeks 12 and 24)
- MRU (no longer required per Amendment 5)

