7.3.2.6. Weeks 36 until Discontinuation of Treatment, every 12 weeks

The following procedures will be performed:

- Physical examination
- Eye-related symptoms (every 12 weeks until 18 months, then once every 24 weeks)
- Disease-related symptoms (no longer required per Amendment 5)
- Vital signs
- ECOG performance status
- PRO assessments
- Concomitant medications
- Adverse events
- Hematology
- Serum chemistry
- Serum immunoglobulins and β_2 -microglobulin
- T/B/NK cells
- Flow cytometry-based immunophenotype assays
- Predictive biomarkers and mechanisms of resistance
- MRU (no longer required per Amendment 5)

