7.3.2.8. End-of-Treatment Visit

The following will be performed 30 (\pm 3) days after the discontinuation of treatment with study drug:

- Physical examination
- Vital signs
- ECOG performance status
- Eye-related symptoms

- Disease-related symptoms (no longer required per Amendment 5)
- PRO assessments
- Concomitant medications
- Adverse events
- MRU (no longer required per Amendment 5)
- Hematology
- Serum chemistry
- Flow cytometry-based immunophenotype assays
- Predictive biomarkers and mechanisms of resistance

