7.3.4.2. Next-line Ibrutinib Therapy Treatment Phase

Refer to the next-line ibrutinib therapy Schedule of Assessments ([Appendix M](#)) for a complete list of procedures to be performed at each scheduled study visit.

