Appendix L: Child-Pugh Score for Subjects with Liver Impairment

Measure	1 point	2 points	3 points
Total bilirubin, $\mu\text{mol/L}$ (mg/dL)	<34 (<2)	34-50 (2-3)	>50 (>3)
Serum albumin, g/L (g/dL)	>35 (>3.5)	28-35 (2.8-3.5)	<28 (<2.8)
PT/INR	<1.7	1.71-2.30	>2.30
Ascites	None	Mild	Moderate to Severe
Hepatic encephalopathy	None	Grade I-II (or suppressed with medication)	Grade III-IV (or refractory)

Points	Class
5-6	A
7-9	B
10-15	C

Source:

Appendix M: Schedule of Assessments for Patients Treated with Ofatumumab who are to Receive Next-line Ibrutinib Therapy

Study Weeks	Assessment for Next-line Ibrutinib Therapy	Treatment Phase			Follow-up Phase
		Every 4 weeks for 24 weeks	Every 12 weeks until PD	End-of-Treatment Visit	Follow-up (Every 12 weeks)
Study Windows	±14 d	±7 d	±7 d	30 (±3 d)	±7 d
Study Drug Administration					
Ibrutinib 420 mg per day PO		Continuous Daily Dosing			
Procedures					
Medical Monitor approval	X				
Concomitant medications	X	X	X	X	
Adverse events		X	X	X	
Physical examination, vital signs, ECOG	X	X	X	X	
Hematology	X	X ^e	X	X	
Serum chemistry	X				
PK sampling if on CYP3A4/5 inhibitors ^d					
Disease assessment:					
Investigator assessment of response and for progression ^a			X		
Predictive biomarkers			X ^b		
Survival status					X ^c
Subsequent anticancer therapies					X ^c

CLL=chronic lymphocytic leukemia; d=day; ECOG=Eastern Cooperative Oncology Group; IRC=Independent Review Committee; PD=progressive disease; PO=oral; qd=once daily

- a. Efficacy assessments should include CT scan annually until the first disease progression on protocol. For patients who have had experienced PD and are crossed over to ibrutinib, CT scans for response assessments may be performed at investigator's discretion.
- b. Blood samples will be collected at Week 12 Day 1 and at PD
- c. By telephone
- d. Patients who must take strong or moderate CYP3A4/5 inhibitors while on treatment with ibrutinib, additional PK collections for evaluation of ibrutinib exposure is requested at the following scheduled visit after concomitant CYP3A4/5 inhibitor has started and still in use. Please refer to [Section 7.1.21](#) for the PK collection schedules.

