- e. CBC should be performed weekly for the first 4 weeks

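### Appendix M schedules serum chemistry once before crossover ibrutinib and never during it, so the hepatic dose guidance has no scheduled chemistry to prompt it in these patients.

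*Protocol*

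**What the plan says.** Protocol 6.2.6 gives ibrutinib dose guidance for liver impairment that develops during the study: 280 mg daily in Child-Pugh class A, a hold in class C, and for the middle class "For subjects who develop moderate liver impairment while on study (Child-Pugh class B), the recommended dose reduction is to a level of 140 mg" daily. It makes no exception for crossover patients. Protocol 6.2.4 separately requires a hold for any other Grade 4 toxicity and for unmanageable Grade 3 toxicity.

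Under Protocol 7.3.4, ofatumumab patients who go on to ibrutinib follow the table titled "Appendix M: Schedule of Assessments for Patients Treated with Ofatumumab who are to Receive Next-line Ibrutinib Therapy". Section 7.3.4.2 sends the reader to it "for a complete list of procedures to be performed at each scheduled study visit". Its serum chemistry row has one mark, in the column for the assessment before ibrutinib. Its hematology row has four: that column, the every-4-week visits, the every-12-week visits and End of Treatment. Footnote e adds that "CBC should be performed weekly for the first 4 weeks".

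For randomized patients, serum chemistry is listed in 7.3.2.5 ("Week 4-24 Visits, every 4 weeks"), in 7.3.2.6 ("Weeks 36 until Discontinuation of Treatment, every 12 weeks") and in 7.3.2.8, the End-of-Treatment visit 30 (± 3) "days after the discontinuation of treatment with study drug".

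Under Protocol 7.1.18 the chemistry panel supplies albumin, total bilirubin, AST and ALT. Under 7.1.17, PT/INR is drawn at Screening only.

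**The concern.** Crossover patients take the same drug at the same 420 mg dose as the randomized ibrutinib arm, and the same dose-modification rules govern them. Yet once they start, no scheduled blood test reports on the liver. Low albumin, a moderate bilirubin rise or a transaminase rise can all occur without symptoms. Without a scheduled panel, such a change is found only if someone already has a reason to test.

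The protocol itself shows why a delay could matter. Section 1.3.1 reports single-dose ibrutinib AUC raised 2.7-, 8.2- and 9.8-fold in Child-Pugh classes A, B and C. It also reports a higher proportion of Grade 3 or worse adverse reactions in patients with mild hepatic impairment by NCI criteria. A crossover patient with unrecognised impairment would stay on 420 mg where 6.2.6 recommends less.

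This is a patient-safety matter. It does not touch the primary PFS analysis.

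**Working it through.** The plan states no figure to reproduce. The check is a count of scheduled chemistry panels under each schedule, using nominal visit weeks.

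**Randomized ibrutinib** (from the text of 7.3.2.5, 7.3.2.6 and 7.3.2.8):
- Weeks 4, 8, 12, 16, 20, 24 = 6 panels.
- Weeks 36, 48, 60, 72, 84, 96 = 6 more, so 6 + 6 = 12 through Week 96.
- End of Treatment = 1.

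**Crossover ibrutinib** (from Appendix M):
- Chemistry: 1 before ibrutinib, then 0 at every later visit.
- Hematology through Week 24: Weeks 1, 2, 3, 4 (footnote e), then 8, 12, 16, 20, 24 = 4 + 5 = 9 draws.

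| Scheduled on treatment | Randomized ibrutinib | Crossover ibrutinib |
|---|---|---|
| Chemistry through Week 24 | 6 | 0 |
| Chemistry through Week 96 | 12 | 0 |
| Chemistry at End of Treatment | 1 | 0 |
| Longest nominal gap between panels | 4 weeks to Week 24, then 12 weeks | no limit |
| PT/INR after Screening | 0 | 0 |

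The last row shows that PT/INR is not specific to crossover. The crossover gap is the chemistry panel.

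**Is the single mark a product of text extraction?** The Appendix M rows are consistent with one another. Examination, concomitant medication and hematology have four marks starting in the first column. Adverse events have three, starting in the second. Survival status sits in the last. The PK row is blank, but footnote d makes that sampling conditional, so a blank is expected. Appendix A did extract imperfectly: its chemistry row shows six marks where the visit text implies seven (Screening, Weeks 1, 4 and 8, Weeks 12-24, Week 36 onward, End of Treatment). For that reason the randomized counts above come from the text. Appendix M has no visit-by-visit text to check against. Loss of three marks from one row is unlikely but not excluded.

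**Does other text supply the missing tests?** Section 7 allows extra laboratory work on clinical indication. Section 7.3.2 allows local laboratories to guide dosing. Section 6.2.6 asks for monitoring for signs of toxicity. Each permits or encourages testing; none schedules it.

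**Is the omission announced as deliberate?** Where procedures were dropped (disease-related symptoms and resource use), the protocol says so and cites Amendment 5. It says nothing of the kind about chemistry.

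**The case against.** The strongest reply is that 6.2.6 is guidance for impairment already recognised, not a laboratory surveillance rule. A patient with five normal Appendix L inputs scores 5 points, which is class A. If the score alone triggered the rule, every patient with a healthy liver would drop to 280 mg. The protocol also never schedules a complete Child-Pugh score for anyone, because PT/INR stops at Screening. This stands. A reader might infer that counting the albumin and bilirubin combinations that fall in class B measures how many cases would be missed. It does not: the score grades impairment once recognised and gives no frequency.

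Second, crossover patients are not unmonitored. They have a panel and Medical Monitor approval before starting, examination and adverse-event review at treatment visits, and testing on indication. This also stands, but all of it after the first dose depends on a sign or a suspicion.

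Third, Appendix M is a reduced schedule written after the primary endpoint was met, for a drug already approved in CLL/SLL in many regions. Less imaging is understandable in that setting. It does not explain why chemistry is kept for one group on 420 mg and dropped for the other.

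Fourth, a reader might infer from Section 4, where the investigator's assessment includes "review of hematology and serum chemistry results", that crossover response assessment is compromised. The documents do not support that: no response or progression criterion in Table 4 uses a chemistry value.

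**Conclusion.** The point holds as a gap in scheduled safety monitoring: 0 on-treatment chemistry panels for crossover patients against 12 through Week 96 for randomized patients on the same drug and dose, and 0 against 1 at End of Treatment. The hepatic guidance in 6.2.6, and the holds in 6.2.4 so far as they rest on chemistry, have no scheduled result to prompt them in this group.

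It rests on two assumptions: that the extracted Appendix M shows the true marks, and that sites test by the schedule unless they have a reason to do more.

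Its clinical size is unknown. The documents give neither the number of patients on crossover ibrutinib nor the frequency of hepatic impairment. A reader might take the planned minimum of 350 patients, randomized 1:1, to imply up to 175 patients each missing six early panels. That is not supported. The DMC determination was on 3 January 2014, this protocol version cites an August 2016 brochure, and the SAP's final extract is from 26 November 2018. Many crossover patients may have been past Week 24 before any amendment could reach them. The change is worth considering; it is not a defect in the efficacy analysis.

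**What to change.** In Appendix M, mark serum chemistry at the every-4-week, every-12-week and End-of-Treatment visits. Add a footnote calling for PT/INR only when chemistry or examination suggests hepatic impairment, so that a Child-Pugh class can then be assigned under 6.2.6.

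Cost: a protocol amendment and one added panel at each of these visits. A patient starting crossover under the amendment would have 6 panels in the first 24 weeks, then 52/12 ≈ 4.3 a year, plus 1 at End of Treatment. A patient already past Week 24 would have only the later ones. Blood is already drawn at every one of these visits, so no visit or invasive procedure is added. The benefit is confined to patients still on, or starting, crossover ibrutinib when the amendment takes effect.

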6.2.7. Precautions and Adverse Events

The most common treatment-emergent adverse events were diarrhea, fatigue, nausea, cough and anemia. Additional common AEs such as peripheral edema, pyrexia, vomiting, constipation, upper respiratory tract infection, arthralgia, dyspnea, thrombocytopenia, decreased appetite, headache, muscle spasm, neutropenia, contusion, abdominal pain, dizziness, pneumonia, myalgia, and dyspepsia have been reported. In addition, Events of Special Interest are outlined in [Section 9.3.4](#). For complete information on precautions refer to the [IB](#).

6.3. Identification of Investigational Product(s)

6.3.1. Ibrutinib

Ibrutinib is provided as hard gelatin capsules containing 140 mg of ibrutinib. The capsules are packaged in opaque high-density polyethylene (HDPE) plastic bottles with labels bearing the appropriate label text as required by governing regulatory agencies. The drug product is manufactured for Pharmacyclics LLC by a contract manufacturer. All formulation excipients are compendial and are commonly used in oral formulations.

The recommended storage condition for ibrutinib capsules is controlled room temperature. Formal International Conference on Harmonization (ICH) stability studies are ongoing to determine the shelf-life of the product. Please refer to the Pharmacy Binder and study drug label for more detailed information.

Refer to the [IB](#) for additional information regarding the drug product to be used in this study.

6.3.2. Ofatumumab

Ofatumumab, manufactured by GlaxoSmithKline, is provided in solution in single-use vials. Refer to the local ofatumumab package insert for details.

6.4. Treatment Compliance

Patient compliance with ibrutinib will be assessed by the site pharmacist or designee at each visit using direct questioning, examination of patient diaries, and capsule counts. Ofatumumab compliance will be performed by the site pharmacist or designee as patients will not be taking the study drug home.

Compliance will be verified by the Sponsor or designee and will be recorded in the study Pharmacy Binder. The pharmacist or designee will:

- Maintain records of product delivery, inventory, return, and destruction
- Maintain temperature monitoring
- Maintain up-to-date accountability of the study drug in the study drug accountability log (or equivalent)
- Document the use of study product by each patient
- Return or destroy unused study product as per Sponsor's instructions

6.5. Randomization and Blinding

A minimum of 350 patients will be randomized in a 1:1 ratio to each of the 2 treatment arms in this study. Randomization will be used to minimize bias in the assignment of patients to the 2 treatment arms. Two randomization schemes will be generated: one for each geographic region (North America versus Rest of World). Under each scheme, randomization will be

stratified using the following two factors: 1) presence versus absence of refractory disease to purine analog and anti-CD20 containing chemoimmunotherapy regimen, and 2) presence versus absence of 17p del.

This is an open-label study; neither patients nor Investigators will be blinded to treatment.

The primary efficacy evaluation will be performed by an IRC, which will be blinded to study treatment information and lymphocyte count.

6.6. Concomitant Therapy

6.6.1. Concomitant Medications to be Used With Caution

Antiemetics are permitted if clinically indicated. Standard supportive care medications are permitted; this includes pre-medication for ofatumumab infusion as per the ofatumumab package insert. Use of neutrophil growth factors (filgrastim and pegfilgrastim) is permitted per the American Society of Clinical Oncology (ASCO) guidelines ([Smith 2006](#)).

For patients considered at risk for tumor lysis syndrome (TLS):

Patients with more than one of the following factors are considered to be at increased risk of TLS and should be considered for hydration and treatment with an uric acid lowering agent (xanthine oxidase inhibitor allopurinol or Uloric [febuxostat] +/- rasburicase per the drug products package insert) prior to treatment with study drug, as well as for frequent monitoring of tumor lysis associated signs and symptoms.

- Serum creatinine $\geq 1.5x$ ULN
- WBC $\geq 50,000/mm^3$
- Uric acid $>$ ULN

6.6.1.1. Guideline for Use of CYP Inhibiting/Inducing Drugs

Ibrutinib is metabolized primarily by CYP3A4. Avoid co-administration with strong or moderate CYP3A inhibitors and consider alternative agents with less CYP3A inhibition. Co-administration of ketoconazole, a strong CYP3A inhibitor, in 18 healthy subjects increased dose normalized exposure, C_{max} and AUC_{0-last} , of ibrutinib by 29- and 24-fold, respectively. The maximal observed ibrutinib exposure (AUC) was ≤ 2 -fold in 37 patients treated with mild and/or moderate CYP3A inhibitors when compared with the ibrutinib exposure in 76 patients not treated concomitantly with CYP3A inhibitors. Clinical safety data in 66 patients treated with moderate (n=47) or strong CYP3A inhibitors (n=19) did not reveal meaningful increases in toxicities. Strong inhibitors of CYP3A (eg, ketoconazole, indinavir, nelfinavir, ritonavir, saquinavir, clarithromycin, telithromycin, itraconazole, and nefazadone) should be avoided. If a strong CYP3A inhibitor must be used, consider reducing the ibrutinib to 140 mg or withhold treatment temporarily. Subjects should be monitored for signs of ibrutinib toxicity. If the benefit outweighs the risk and a moderate CYP3A inhibitor must be used, reduce ibrutinib to 140 mg for

the duration of the inhibitor use. Monitor subject for toxicity and follow dose modification guidance as needed. For subjects who are already on a moderate CYP3A inhibitor concomitantly with ibrutinib without significant toxicity the investigator may consider the overall risk-benefit to determine if a dose reduction of ibrutinib is appropriate. Avoid grapefruit and Seville oranges during ibrutinib treatment, as these contain moderate inhibitors of CYP3A (see [Section 6.2.1](#)). No dose adjustment is required in combination with weak CYP3A inhibitors.

Co-administration of ibrutinib with strong CYP3A inducer, rifampin, in healthy subjects decrease ibrutinib plasma concentration by approximately 10-fold. Avoid concomitant use of strong CYP3A inducers (eg, carbamazepine, rifampin, phenytoin, and St. John's Wort). Consider alternative agents with less CYP3A induction.

A list of common CYP3A inhibitors and inducers is provided in [Appendix C](#); a comprehensive list of inhibitors, inducers, and substrates may be found at <http://medicine.iupui.edu/clinpharm/ddis/main-table/>. This website is continually revised and should be checked frequently for updates.

